2.7.4.4.2 Subject ADA status

The following overall summaries will be provided using the Immunogenicity incidence set:

- Treatment-boosted ADA-positive: number and percent of subjects with at least one treatment-boosted ADA-positive sample. The denominator is the number of subjects with an ADA-positive sample at baseline.
- Treatment-induced ADA-positive: number and percent of subjects with at least one treatment-induced ADA-positive sample. The denominator is the number of subjects with an ADA-negative sample at baseline.
- ADA-negative: number and percent of subjects with no treatment-induced or treatment-boosted ADA-positive sample.
- ADA incidence (i.e. % ADA-positive): number and percent of subjects with at least one treatment-induced or treatment-boosted ADA-positive sample.

The following summaries, both overall and by time point (including baseline), will be provided using the Immunogenicity prevalence set. For summaries by time point, the denominator is the number of subjects at that time point with determinant samples:

- ADA prevalence: number and percent of subjects with at least one ADA-positive sample.
- NAb ADA prevalence: number and percent of subjects with at least one ADA-positive NAb sample.

A listing will be provided by subject with supporting information (i.e. ADA sample status at each time point (including positive samples) and subject ADA status

2.10 Subject-reported outcomes

The eDiary will collect the following subject-reported outcomes during DB period:

- Modified MIDAS, monthly
- [REDACTED]
- [REDACTED]
- Beck Depression Inventory, screening
- [REDACTED]

Change from baseline in migraine-related disability and productivity as measured by the mMIDAS during the last 4 weeks of the 12-week treatment period is among the secondary endpoints (see [Section 2.6](#)).

Beck Depression Inventory is collected only at screening and reported in baseline disease characteristics (see [Section 2.3.2](#)).

2.11 Other analyses

[figure not shown]

Figure (line plot with confidence interval) will be produced showing the change from baseline in the secondary endpoints (mMIDAS total score and monthly acute headache medication treatment days) at the end of each month by treatment.

Figure (bar plot) will be produced showing the responder rate (at least 50% reduction from baseline in monthly migraine days) at the end of each month by treatment.

2.12 Interim analysis

2.12.1 Blinded Sample Size Re-estimation

To account for potential larger than expected variability during the trial, a blinded interim assessment is planned after about 50% of subjects finish 12 weeks' DB treatment or early withdraw. Only the standard deviation of the primary variable, change from baseline in monthly migraine days in the last 4 weeks, based on pooled (blinded) data from all subjects who had the opportunity to complete the week 12 assessment in the trial, will be estimated. The sample size will be increased appropriately if the standard deviation is larger than 6.8.

The type I error of the primary analysis will be maintained, as the treatment assignment will remain blinded and there is no intention to stop the study early due to efficacy.

2.12.2 Unblinded Interim Analysis

An unblinded IA will be conducted after 70% (385) of subjects have completed the DB treatment period (including early withdrawals), to determine whether the study will stop early or continue to the primary analysis (full sample size in DB period). The following data analysis (excluding OLE period) will be included in IA read-out.

- Subject disposition (as defined in [Section 2.3.1](#))
- Demographics and baseline characteristics (as defined in [Section 2.3.2](#))
- Study treatment / Compliance (as defined in [Section 2.4.1](#))
- The primary and sensitive analysis on key efficacy endpoints:
 - The change from baseline in monthly migraine days in the last 4 weeks of the 12-week treatment period (as defined in [Section 2.5](#))
 - Proportion of subjects who achieve at least a 50% reduction from baseline in monthly migraine days in the last 4 weeks of the 12-week treatment period (as defined in [Section 2.6](#))
 - Change from baseline in monthly acute headache medication days during the last 4 weeks of the 12-week treatment period (as defined in [Section 2.6](#))

- Change from baseline in migraine-related disability and productivity as measured by modified MIDAS during the last 4 weeks of the 12-week treatment period (as defined in [Section 2.6](#))
- The primary analysis on key safety endpoints:
 - Adverse events (as defined in [Section 2.7.1](#))
 - Laboratory evaluations - Hematology, Chemistry and Urinalysis (as defined in [Section 2.7.3](#))
 - ECG evaluations (as defined in [Section 2.7.4.1](#))
 - Vital signs (as defined in [Section 2.7.4.2](#))
- Subgroup analysis in Chinese sub-population: repeat the primary analysis for following efficacy endpoints and safety endpoints
 - The change from baseline in monthly migraine days in the last 4 weeks of the 12-week treatment period (as defined in [Section 2.5](#)). Sensitive analyses for primary endpoint will not be conducted for Chinese sub-population.
 - Proportion of subjects who achieve at least a 50% reduction from baseline in monthly migraine days in the last 4 weeks of the 12-week treatment period (as defined in [Section 2.6](#))
 - Change from baseline in monthly acute headache medication days during the last 4 weeks of the 12-week treatment period (as defined in [Section 2.6](#))
 - Change from baseline in migraine-related disability and productivity as measured by modified MIDAS during the last 4 weeks of the 12-week treatment period (as defined in [Section 2.6](#))
 - Adverse events (as defined in [Section 2.7.1](#))

3 Sample size calculation

The planned total sample size in this proposed China-centric phase 3 study is 550 subjects. The key assumptions in calculating the sample size are based on prior results from erenumab global pivotal study. A treatment difference in terms of change from baseline on MMDs during Week 9-12 (primary endpoint) for erenumab 70 mg vs. placebo is assumed at -2.0 days. The common standard deviation of the primary variable is assumed at 6.8. Given a 1:1 randomization ratio among erenumab 70 mg and placebo, it requires a total of 550 subjects (including 10% drop out rate) to achieve approximate 90% power to demonstrate the treatment difference of erenumab 70 mg compared with placebo under two-sided 0.05 alpha level. The impact of spending alpha at unblinded interim analysis on sample size and power is relatively negligible. Having this interim analysis with alpha spending at 0.014 two-sided, at final analysis an observed p-value ≤ 0.046 two-sided would be required (given that the interim analysis was performed when 70% subject finished treatment or early withdraw). With that said, the overall power will be maintained at approximately 88% with planned sample size.

The sample size for Chinese sub-population will make sure the consistency of treatment effect between Chinese and total population. The methods for consistency assessment are proposed as,

$\Pr(D_{\text{China}} / D_{\text{overall}} > 0.5) > 95\%$,

which means that this China study should have high probability ($>95\%$) to demonstrate consistency where the treatment effect (treatment difference of erenumab compared with placebo) observed in the Chinese population should be as high as at least 50% of the treatment effect observed in the overall study population in the prospective trial, assuming there is no difference between the Chinese population assessed in the trial and the overall population.

To meet the above criteria, approximately 350 (out of 550 for the overall study) Chinese subjects will be recruited.

At the interim analysis, as long as China population takes the majority of the overall population, there should have high likelihood to demonstrate the consistency as well.

4 Change to protocol specified analyses

Not applicable.

5 Appendix

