**Section 12.8.1 Primary endpoint(s)**

Overall power updated from 88 to 90%.

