If it is decided to stop early due to **success** (positive IA read-out), all subjects ongoing in the double-blind treatment period at the time of the IA read-out will be scheduled for an End of Treatment visit: they will then either enter into the open-label treatment period or enter into the safety follow-up Period (in case the subject does not want to continue in the open-label treatment period).

In case of a **negative** interim analysis (70%) which is meeting the futility boundary, or in case of a negative primary analysis at the full sample size (100%), the open-label treatment period will be cancelled. All subjects ongoing in the double-blind treatment period at that time will be scheduled for an End of Treatment visit followed by a safety follow-up visit. All subjects ongoing in the open-label treatment period will be scheduled for an End of Treatment Open-Label visit.

If it is decided to continue until final analysis, the recruitment will continue to full sample size.

In case of exceptionally fast recruitment the unblinded IA might be cancelled and the full sample size will be analyzed.

[figure not shown]
Two clinical study reports (CSR) are planned for this study:

- An **interim CSR** will be prepared for the **primary analysis**, when the last patient completed the double-blind treatment period (including early withdrawals). This might either be after approximately 70% of subjects completed the double-blind treatment period, or when 100% of subjects completed the double-blind treatment period. The CSR will include efficacy and safety data, as well as safety follow-up visit data up to this point. This CSR will be prepared for regulatory submission in China.
- A **final CSR** will be prepared when all subjects have completed their respective last visit (LPLV). In this CSR, all available data not captured in the interim CSR will be included.

In case of a **negative** primary analysis only one CSR will be developed, including all available double-blind, safety follow-up and open-label treatment data.

If the marketing application of erenumab, for the indication in this study, is rejected in a participating country, the subjects in that country will be discontinued from the open-label treatment period. End of Trial will occur when the last subject completes the last visit (Last patient Last Visit (LPLV)) of the trial.

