## 12.8 Sample size calculation

### 12.8.1 Primary endpoint(s)

The planned total sample size in this proposed China-centric phase 3 study is 550 subjects. The key assumptions in calculating the sample size are based on prior results from erenumab global pivotal study. A treatment difference in terms of change from baseline on MMDs during Week 9-12 (primary endpoint) for erenumab 70 mg vs. placebo is assumed at -2.0 days. The common standard deviation of the primary variable is assumed at 6.8. Given a 1:1 randomization ratio among erenumab 70 mg and placebo, it requires a total of 550 subjects (including 10% drop out rate) to achieve approximate 90% power to demonstrate the treatment difference of erenumab 70 mg compared with placebo under two-sided 0.05 alpha level. The impact of spending alpha at unblinded interim analysis on sample size and power is relatively negligible. Having this interim analysis with alpha spending at 0.014 two-sided, at final analysis an observed p-value

$\leq 0.046$  two-sided would be required (given that the interim analysis was performed when 70% subject finished treatment or early withdraw). With that said, the overall power will be maintained approximately at 90% with planned sample size.

The sample size for Chinese sub-population will make sure the consistency of treatment effect between Chinese and total population. The methods for consistency assessment is proposed as,

$$\Pr(D_{\text{China}} / D_{\text{Overall}} > 0.5) > 95\%,$$

which means that this China study should have high probability ( $>95\%$ ) to demonstrate consistency where the treatment effect (treatment difference of erenumab compared with placebo) observed in the Chinese population should be as high as at least 50% of the treatment effect observed in the overall study population in the prospective trial, assuming there is no difference between the Chinese population assessed in the trial and the overall population.

To meet the above criteria, approximately 350 (out of 550 for the overall study) Chinese subjects will be recruited.

At the interim analysis, as long as China population takes the majority of the overall population, there should have high likelihood to demonstrate the consistency as well.

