MAR	Missing at Random
MCMC	Markov Chain Monte Carlo
MedDRA	Medical Dictionary for Drug Regulatory Affairs
MI	Multiple Imputation
MIN	Minimum function
mMIDAS	Modified Migraine Disability Assessment
MNAR	Missing Not at Random
NRI	Non-Responder Imputation
OLE	Open-label extension
PD	Protocol Deviations

PRO	Subject-Reported Outcomes
PT	Preferred Term
qm	once a month
SAE	Serious Adverse Event
SAF	SAFety analysis set
SAP	Statistical Analysis Plan
sc	Subcutaneous
SD	Standard Deviation
SOC	System Organ Class
SSAP	Supplemental Statistical Analysis Plan
TEAE	Treatment-Emergent Adverse Event
TFLs	Tables, Figures, Listings
ULN	Upper Limit of Normal
UN	Unstructured covariance matrix
US	United States
VAS	Visual Analog Scale
VS	Vital Signs
WHO	World Health Organization

1 Introduction

The purpose of this statistical analysis plan (SAP) is to provide details of the statistical analysis according to Section 12 of the study protocol (**v02**) for AMG 334 Study CAMG334A2304 dated 26 Jan 2021 and along with any additional analyses, specifications or deviations from the protocol planned.

The scope of this plan includes the primary, secondary, [REDACTED] analyses, which will be executed by Novartis internal statisticians and programmers, if not specified differently. Those analyses will be reported in the CSR.

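### SAP section 3 states about 88% overall power, but its own inputs give 90.2% without futility stopping, in line with the protocol's figure of about 90%

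*SAP*

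**What the plan says.** SAP section 3 fixes the total at 550 ("The planned total sample size in this proposed China-centric phase 3 study is 550 subjects"), including 10% drop-out, with 1:1 allocation. The treatment difference "for erenumab 70 mg vs. placebo is assumed at -2.0 days", and "The common standard deviation of the primary variable is assumed at 6.8". It says this gives roughly 90% power at two-sided 0.05. It then introduces the unblinded interim analysis, with two-sided levels of 0.014 at 70% and 0.046 at the end, describes the interim's cost in power and sample size as minor, and concludes that "the overall power will be maintained at approximately 88% with planned sample size".

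Protocol section 12.8.1 runs through the same inputs in nearly the same words but concludes that "the overall power will be maintained approximately at 90% with planned sample size".

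The SAP introduction ties the SAP to protocol version 02, "for AMG 334 Study CAMG334A2304 dated 26 Jan 2021", and SAP section 4 declares no change to the protocol-specified analyses. The protocol's own summary of changes for that version records "Overall power updated from 88 to 90". That entry describes superseded text and is cited only as the likely source of the 88%. The discrepancy is between the current SAP and the current protocol.

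Protocol section 3 also refers to a negative "interim analysis (70%) which is meeting the futility boundary" but gives no value for the boundary. The sample size text in both documents mentions only alpha spending.

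**The concern.** Two current documents give different overall power for one design with one set of inputs, so at most one figure can be right. The SAP paragraph is also hard to reconcile with itself: it starts from about 90%, calls the effect of the interim minor, and ends at 88%.

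What is at stake is limited. Planning power enters no test, boundary or decision rule. It is, however, a design characteristic that would be reported in a clinical study report intended for regulatory submission, and the SAP's figure would be wrong there.

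**Working it through.** **Inputs** (identical in SAP section 3 and protocol section 12.8.1): N = 550, drop-out 10%, 1:1 allocation, difference 2.0 days in absolute value, SD 6.8, two-sided levels 0.014 at information fraction 0.7 and 0.046 at the end.

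**Step 1: reproduce the sample size.** For 90% power at two-sided 0.05, n per arm = 2 × 6.8² × (1.960 + 1.282)² / 2.0², which rounds up to 243. That is 486 in total, and 486 / 0.9 = 540. The planned 550 is slightly above this, so the stated sample size is sound.

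**Step 2: fixed-design power.** Evaluable subjects = 550 × 0.9 = 495. Expected z at the end = 2.0 / (6.8 × √(4/495)) = 3.272. Power at 0.05 = Φ(3.272 − 1.960) = 90.5%. With the noncentral t distribution it is 90.4%. This matches the figure of about 90% that both documents give before the interim is considered.

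**Step 3: two-look power.** The critical values are z₁ = 2.457 (0.014) and z₂ = 1.995 (0.046). The two statistics have correlation √0.7, and the expected interim z is 3.272 × √0.7 = 2.737.

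- Rejection at the interim: Φ(2.737 − 2.457) = 61.0%.
- Overall: 1 − P(Z₁ < z₁ and Z₂ < z₂) from the bivariate normal = 90.2%.
- Final look taken alone at 0.046: Φ(3.272 − 1.995) = 89.9%. This is not overall power, because it leaves out trials that reject only at the interim.
- Overall two-sided type I error at these levels: 0.0501, which is 0.05 up to rounding of the thresholds.

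The interim costs about 0.3 points (90.5% to 90.2%), which agrees with the documents' description of its cost as minor. A fall to 88% would be 2.5 points.

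**Step 4: sensitivity to the boundary.** Recomputed Lan-DeMets O'Brien-Fleming levels (0.0148 and 0.0455) give 90.1%. Classic O'Brien-Fleming levels (0.0164 and 0.0446) also give 90.1%.

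**Step 5: what 88% would require.** Changing one input at a time, without futility stopping unless stated:

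| Change | Value needed for 88% | Value in the documents |
|---|---|---|
| Evaluable subjects | 460 (16.4% drop-out) | 495 (10%) |
| SD | 7.05 | 6.8 |
| Difference | -1.93 | -2.0 |
| Single final look | level 0.036 (0.05 − 0.014) | 0.046 |
| Futility stop at interim z below | about 1.27 | mentioned in protocol section 3, no value |

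**Step 6: range for the unstated futility boundary.** These boundaries are assumptions, with the efficacy thresholds left unchanged. Power = P(Z₁ ≥ z₁) + P(c < Z₁ < z₁ and Z₂ ≥ z₂).

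| Stop if interim z is below c | Overall power |
|---|---|
| 0 | 90.2% |
| 0.5 | 90.1% |
| 1.0 | 89.3% |
| 1.25 | 88.1% |
| 1.3 | 87.7% |

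**The case against.** The strongest reply has three parts.

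First, the figure is given as approximate, and the gap is 2.2 points from the two-look power and only 1.9 from the final look alone. But the same SAP paragraph treats about 90% and about 88% as two different numbers, and the sponsor thought the difference worth changing in the protocol. Even the final look alone rounds to 90%.

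Second, a futility rule could account for 88%. The protocol mentions a futility boundary, and the detailed decision algorithms are assigned to the DMC charter, which is not among the documents. This cannot be ruled out, and it is why the 90.2% is stated as the power without futility stopping. Nothing in the SAP power sentence supports it, however: that sentence rests on alpha spending alone, and a boundary at z of 1.0 or lower would leave power at 89.3% or more.

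Third, nothing depends on the number. Under SAP section 2.12.1 the blinded re-estimation is triggered by an SD above 6.8, not by a power target, and a reader holding both documents can infer that 90% is the current figure. This part stands. It limits the weight of the point but does not make the SAP figure correct.

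**Conclusion.** The concern holds. From its own stated inputs, SAP section 3 should report about 90% overall power (90.2% by calculation), not about 88%. It also conflicts with the protocol version it says it implements.

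The result assumes a normal approximation, 495 evaluable subjects, an interim at exactly 70% information and no futility stopping. The size is about 2 points, in the conservative direction. The sample size of 550, the 0.014 and 0.046 thresholds and the planned analyses are unaffected. The figure of 88% most likely survives from the protocol text before Amendment 02, but the finding does not depend on that.

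**What to change.** In SAP section 3, replace the 88% with approximately 90%, so that it agrees with protocol section 12.8.1. If 88% was calculated with an input not stated there, for example a futility boundary, state that input and its value in both documents and give the same overall power in both.

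The correction is one line in the SAP and has no effect on sample size, boundaries or analysis. Only the alternative route would also require a change to the protocol text.

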5.1 Imputation rules

Subjects may miss specific data points for a variety of causes. In general, data could be missing due to a subject's early withdrawal from study, a missed visit, or inability to evaluate an endpoint at a particular point in time. For this study, most of the efficacy endpoint will be collected via eDiary and subjects could miss entering several days of data in each 28-consecutive day interval. The general procedures outlined below describe what will be done when a data point is missing.

5.1.1 Study drug

Date of first study drug administration (Day 1)

Day 1 is defined as the first day of administration of randomized study drug (AMG334 or matching placebo). All other days will be labeled relative to Day 1. If subject will not be dosed at Day 1, the Study Day 1 is defined as day of randomization.

Date of last study drug administration

The date of last dose of randomized study drug is simply the day of the last dose.

5.1.2 AE and Concomitant medication date imputation

Missing or incomplete dates will be listed as it is in any listings.

Incomplete start date of an adverse event or concomitant medication taken will be handled by following rule:

	Missing	Imputation	Exception
Start date (AE, concomitant medication)	Day	01	Default to Study Day 1 if an adverse event starts the same year and month as Study Day 1
	Day/Month	01Jan	Default to Study Day 1 if an event started the same year as Study Day 1
	Day/Month/Year	No imputation	

